5.1.4 Visit Procedures

Medical procedures (examinations, injections, etc.) must be conducted by appropriately licensed or credentialed study site staff working within the scope of their license / credentials.

D0 Visit: Inclusion, Randomization, Blood Sample, and Vaccination

1. **Subjects aged 13 to < 18 years^a:** Give the subject and the subject's parent / guardian information about the trial, answer any questions, obtain signed assent from subjects and the written informed consent (signed as below) from the subject's parent / guardian, and give him / her a signed copy of each.
Subjects aged 18 years^a and older: Give the subject information about the trial, answer any questions, obtain signed informed consent form from subject, and give him / her a signed copy.
2. Check inclusion and exclusion criteria for eligibility
3. Collect demographic data
4. Urine pregnancy test (if applicable)
5. Obtain verbal medical history about the subject
6. Conduct a history-directed physical examination, including temperature (a physical examination conducted during the same day as part of routine clinical care may be used for this purpose)
7. Contact the interactive response technology (IRT) system for randomization (except for subjects primed with Menveo vaccine which are allocated automatically to Group 2), allocation of subject number, vaccine group assignment, and blood sample subset assignment
8. Obtain the blood sample (see [Section 7.1](#) for detailed instructions regarding the handling of blood samples). If attempts to obtain the first blood draw are unsuccessful (3 attempts), then Visit 1 can be rescheduled to a later date at which point informed consent and

^a Or legal age of majority, if different from 18 years of age

inclusion/exclusion criteria must be re-validated. If the first blood draw cannot be obtained, the subject will be withdrawn from the study without being vaccinated.

9. Administer the MenACYW conjugate vaccine in the deltoid muscle. For subjects in Group 3 and Group 4, administer the concomitant vaccine in the opposite arm.
10. Keep the subject under observation for 30 minutes and record any AE in the source document.
11. Give the subject or subject's parent / guardian a diary card, a thermometer, and a ruler, and go over the instructions for their use.

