12.1.2 Hypotheses and Statistical Methods for Secondary Objectives

No hypotheses will be tested. Descriptive statistics will be presented.

12.1.2.1 Secondary Objective 1

Six days after the administration of MenACYW conjugate vaccine, the hSBA vaccine seroresponse rates, seroprotection rates (hSBA titer $\geq 1:8$), and hSBA GMTs between a subset of 50 subjects per Group 1 and Group 2 will be summarized and geometric mean titer ratio (GMTR) between the subset of 50 subjects per Group 1 and Group 2 will be calculated, and 95% CI will be provided.

12.1.2.2 Secondary Objective 2

Thirty days after the administration of MenACYW conjugate vaccine alone, the hSBA vaccine seroresponse rates, seroprotection rates (hSBA titer $\geq 1:8$), and the hSBA GMTs will be summarized and GMTR between Group 1 and Group 2 will be calculated, and 95% CI will be provided.

12.1.2.3 Secondary Objective 3

Before the administration of MenACYW conjugate vaccine alone, 3-6 years after receiving the primary MCV4 vaccination, the hSBA GMTs will be summarized as well as seroprotection rates (hSBA titer $\geq 1:8$), and GMTR between Groups 1, 3 and 4 and Group 2 will be calculated, and 95% CI will be provided.

12.1.2.4 Secondary Objective 4

At baseline and D30 in subjects after having received a single dose of either MenACYW conjugate vaccine or Menveo vaccine, as part of study MET50 or MET43, the hSBA GMTs will be summarized as well as seroprotection rates (hSBA titer $\geq 1:8$), and GMTR between MenACYW conjugate vaccine and Menveo vaccine groups will be calculated, and 95% CI will be provided. The GMTR between D0 of MET59 and D30 of MET50 (or MET43, if applicable) within MenACYW conjugate vaccine and Menveo vaccine groups will also be calculated, and 95% CI will be provided.

12.1.2.5 Secondary Objective 5

Thirty days after the administration of MenACYW conjugate vaccine when administered alone or concomitantly with Trumenba vaccine or Bexsero vaccine vaccines, the vaccine seroresponse, seroprotection (hSBA titer $\geq 1:8$), and hSBA GMTs will be summarized and GMTR between Group 1 and Group 3, between Group 1 and 4, and between Group 1 and pooled Groups 3 and 4 will be calculated, and 95% CI will be provided.

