3.1 Trial Design

The MET59 study is a Phase IIIb, open-label (the laboratory technicians will be blinded to group assignment), partially randomized, parallel-group, active-controlled, multi-center study to evaluate the antibody persistence 3-6 years after the priming vaccination with either MenACYW conjugate vaccine or the licensed Menevo vaccine, and to evaluate the immunogenicity and safety of a booster dose of MenACYW conjugate vaccine when administered alone or concomitantly with licensed MenB vaccines in adolescents and adults in the US and Puerto Rico.

A total of 600 subjects who were vaccinated 3-6 years earlier in study MET50 are planned to be enrolled. Approximately 400 healthy adolescents and adults who had received 1 dose of either MenACYW conjugate vaccine (Group 1, N=200) or Menveo vaccine (Group 2, N=200) as part of the MET50 study will receive a booster vaccination with MenACYW conjugate vaccine. Approximately 200 healthy adolescents and adults who had received 1 dose of MenACYW conjugate vaccine will receive a booster vaccination with MenACYW conjugate vaccine administered concomitantly with a MenB vaccine (Group 3, MenACYW conjugate vaccine + Trumenba vaccine, N=100; and Group 4, MenACYW conjugate vaccine + Bexsero vaccine, N=100). If needed to meet enrollment requirements, MenACYW conjugate vaccine-primed subjects from the MET43 study could also be considered as source of subjects to be enrolled in Group 1, 3, or 4. Additionally, the population of Menveo vaccine-primed subjects could be enriched with individuals who received 1 dose of Menveo vaccine 3-6 years prior to enrollment in this trial as part of their regular adolescent vaccination schedule and who are 13-25 years of age; ie, non-MET50 subjects).

MenACYW conjugate vaccine-primed subjects (from either MET50 or MET43) will be randomized in a 2:1:1 ratio to receive 1 dose of MenACYW conjugate vaccine alone (Group 1) or to receive 1 dose of MenACYW conjugate vaccine concomitantly with 1 dose of a licensed MenB vaccine (Trumenba vaccine [Group 3] or Bexsero vaccine [Group 4]).

Subjects primed with Menveo vaccine in MET50 or outside of Sanofi Pasteur trials will be assigned to Group 2 (these subjects will not be randomized).

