3.2 Trial Plan

Eligible subjects will be identified and recruited. Subjects who are ≥ 13 to < 18 years of age will sign an Assent Form and their parent / guardian will sign and date the Informed Consent Form (ICF) before any procedure or treatment associated with the trial is performed. Subjects who are 18 years of age and older will sign and date the ICF before any procedure or treatment associated with the trial is performed.

Vaccination

MenACYW conjugate vaccine-primed subjects (from either MET50 or MET43) will be randomized in a 2:1:1 ratio to receive 1 dose of MenACYW conjugate vaccine alone (Group 1) or to receive 1 dose of MenACYW conjugate vaccine concomitantly with 1 dose of a licensed MenB vaccine (Trumenba vaccine [Group 3] or Bexsero vaccine [Group 4]). Subjects primed with Menveo vaccine in MET50 or outside of Sanofi Pasteur trials will be assigned to Group 2 (these subjects will not be randomized). Study vaccines will be administered according to the following schedule:

Group 1:	MenACYW conjugate vaccine on D0	(n=200)
Group 2:	MenACYW conjugate vaccine on D0	(n=200)
Group 3:	MenACYW conjugate vaccine + Trumenba vaccine on D0	(n=100)
Group 4:	MenACYW conjugate vaccine + Bexsero vaccine on D0	(n=100)

Note: In order to comply with the US Food and Drug Administration (FDA)-approved schedules for the respective MenB vaccines, subjects in Group 3 and Group 4 may choose to receive the second dose of MenB vaccine at Visit 2 (D30) after all the study procedures have been completed. Subjects in Group 3 should receive a third dose (or second dose if the alternate 2-dose Trumenba vaccine schedule is used instead by the study Investigators) of Trumenba vaccine on D180, which is not a study visit. These vaccinations for completion of the MenB schedules will take place outside of the objectives and scope of this study and thus will not be described in this SAP.

Blood Sampling

All subjects will provide a pre-vaccination (baseline) blood sample on D0 and a post-vaccination blood sample on D30 (+ 14 days) (for subjects in Group 3 and Group 4, the post-vaccination blood sample will be provided prior to receiving a second dose of MenB vaccine on D30). A subset of the first 50 subjects enrolled in Groups 1 and 2 (total of 100 subjects) will provide an additional post-vaccination blood sample on D06 (± 1 day). This subset will have 3 visits in total.

Collection of Safety Data

Safety data will be collected as follows:

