4.4 Derived Endpoints: Calculation Methods

4.4.1 Immunogenicity

4.4.1.1 Computed Values for Analysis

In order to appropriately manage extreme values (< LLOQ and \geq upper limit of quantitation [ULOQ]) for analysis purposes, the following computational rule is applied to the values provided in the clinical database for each blood sample drawn:

- If a value is < LLOQ, then use the computed value LLOQ/2
- If a value is between \geq LLOQ and < ULOQ, then use the value
- If a value is \geq ULOQ, then use the computed value ULOQ

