4.4.3.5 Protocol-prohibited Therapy, Medication or Vaccines

In general, the “prohibited” variable is not derived. All concomitant medications are reviewed by the clinical team and the value of “prohibited” variable is determined before database lock by the clinical team according to the following rules:

Only two categories of reportable medications will be considered as prohibited/restricted therapy, medication or vaccine:

Category 2:

- Flu vaccines administered within 14 days pre or post each trial vaccination, including the day of the study visit vaccination
- Other vaccines not included as study vaccines, it means non-study vaccines (e.g. Oral poliovirus, Yellow fever, Japanese encephalitis, or other routine/not-routine vaccine not described in the protocol) within the 28 days (4 weeks) preceding or after the trial vaccination, including the day of the study visit vaccination
- Immune globulins, blood or blood-derived products and Immunosuppressive therapy, as described in the protocol

Category 3:

- Antibiotics that the subject received within the 72 hours preceding each Visit for blood draw related to IMP assessment (meningococcal vaccines)

If the above protocol-prohibited therapy, medication or vaccines are received at specific visits, it will impact the corresponding immunogenicity analyses.

The impact on each Per-Protocol Analysis Set (PPAS) is determined as the following:

- If the above protocol-prohibited therapy, medication or vaccines are received at D0 or D06, it will impact PPAS1.
- If the above protocol-prohibited therapy, medication or vaccines are received at D0 or D30, it will impact PPAS2.

5 Statistical Methods and Determination of Sample Size

The statistical analyses will be performed under the responsibility of the Sponsor's Biostatistics platform using SAS® Version 9.4 software or later.

The results of the statistical analysis will be available in the final Clinical Study Report (CSR).

For descriptive purposes, the following statistics in [Table 5.1](#) will be presented. The confidence interval (CI) for the single proportion will be calculated using the exact binomial method (Clopper-Pearson method, quoted by Newcombe [\(14\)](#), ie, using the inverse of the beta integral with SAS®). The CI of the difference in percentages will be computed using the Wilson Score method without continuity correction [\(15\)](#).

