For immunogenicity results, assuming that Log10 transformation of the titers / data follows a normal distribution, at first, the mean and the 95% CI will be calculated on Log10 (titers / data) using the usual calculation for normal distribution (using Student's t distribution with n-1 degree of freedom), then antilog transformations will be applied to the results of calculations, in order to provide geometric means and their 95% CI.

Table 5.1: Descriptive statistics produced

Baseline characteristics and follow-up description	Categorical data	Number of subjects Percentage of subjects
	Continuous data	Mean, standard deviation, quartiles, minimum, and maximum
Clinical safety results	Categorical data	Solicited: Number and percentage (95% CIs) of subjects Unsolicited: Number and percentage (95% CIs) of subjects, and number of events
Immunogenicity results	Categorical data (seroresponse, seroprotection, cutoff)	Number and percentage (95% CIs) of subjects
	Continuous data (titer / concentration)	Log10: Mean and standard deviation Anti-Log10 (work on Log10 distribution, and anti-Log10 applied): Geometric mean, and 95% CI of the geometric mean Graphical representation by Reverse Cumulative Distribution Curve (RCDC)

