5.1.2.2 Statistical Methods

5.1.2.2.1 For Secondary Objective 1

Six days after the administration of MenACYW conjugate vaccine, the hSBA vaccine seroresponse rates, seroprotection rates (hSBA titer $\geq 1:8$), and hSBA GMTs between a subset of 50 subjects per Group 1 and Group 2 will be summarized and geometric mean titer ratio (GMTR) between the subset of 50 subjects per Group 1 and Group 2 will be calculated, and 95% CI will be provided.

5.1.2.2.2 For Secondary Objective 2

Thirty days after the administration of MenACYW conjugate vaccine alone, the hSBA vaccine seroresponse rates, seroprotection rates (hSBA titer $\geq 1:8$), and the hSBA GMTs will be summarized and GMTR between Group 1 and Group 2 will be calculated, and 95% CI will be provided.

5.1.2.2.3 For Secondary Objective 3

Before the administration of MenACYW conjugate vaccine alone, 3-6 years after receiving the primary MCV4 vaccination, the hSBA GMTs will be summarized as well as seroprotection rates (hSBA titer $\geq 1:8$) and GMTR between Groups 1, 3, and 4 and Group 2 will be calculated, and 95% CI will be provided.

5.1.2.2.4 For Secondary Objective 4

At baseline and D30, in subjects after having received a single dose of either MenACYW conjugate vaccine or Menveo vaccine, as part of study MET50 or MET43, the hSBA GMTs will be summarized as well as seroprotection rates (hSBA titer $\geq 1:8$) and GMTR between MenACYW conjugate vaccine and Menveo vaccine groups will be calculated, and 95% CI will be provided. The GMTR between D0 of MET59 and D30 of MET50 (or MET43, if applicable) within MenACYW conjugate vaccine and Menveo vaccine groups will also be calculated, and 95% CI will be provided.

5.1.2.2.5 For Secondary Objective 5

Thirty days after the administration of MenACYW conjugate vaccine when administered alone or concomitantly with Trumenba vaccine or Bexsero vaccine, the vaccine seroresponse, seroprotection (hSBA titer $\geq 1:8$), and hSBA GMTs will be summarized and GMTR between Group 1 and Group 3, between Group 1 and Group 4, and between Group 1 and pooled Groups 3 and 4 will be calculated, and 95% CI will be provided.

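### Optional gain: the randomised D30 GMT ratios of Group 1 v Groups 3 and 4 could be adjusted for the D0 titer; the precision gained is unknown and may be near zero

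*SAP*

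**What the plan says.** SAP 5.1.2.2.5 plans, at D30, the "GMTR between Group 1 and Group 3, between Group 1 and Group 4, and between Group 1 and pooled Groups 3 and 4", each with a 95% CI. Protocol 12.1.2.5 matches it ("between Group 1 and 4, and between Group 1 and pooled Groups 3 and 4 will be calculated"). Neither names a model or a covariate.

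The interval methods given for GMTs are for one group at a time. SAP Section 5 works on log10 titers, "using the usual calculation for normal distribution (using Student's t distribution with n-1 degree of freedom", and SAP 5.1.3.2 uses a normal approximation. A two-group method is stated only for percentages: "The CI of the difference in percentages will be computed using the Wilson Score method without continuity correction" (SAP Section 5).

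Two design features matter here.

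- MenACYW-primed subjects "will be randomized in a 2:1:1 ratio" to Groups 1, 3 and 4 (SAP 3.1).
- A D0 titer is planned for everyone: "All subjects will provide a pre-vaccination (baseline) blood sample on D0" (SAP 3.2). Protocol 5.1.4 adds: "If the first blood draw cannot be obtained, the subject will be withdrawn from the study without being vaccinated".

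Titers below the LLOQ are set to half of it. For titers at or above the upper limit the rule is "then use the computed value ULOQ" (SAP 4.4.1.1). SAP 5.1.2.1 makes the secondary objectives descriptive, without hypotheses.

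**The concern.** In a randomised comparison, a baseline value that predicts the outcome can be used to reduce residual variance. Here that value is already planned, and the plan already uses it for the 4-fold rise and for seroresponse (SAP 4.4.1.3 and 4.4.1.4). As written, the D30 GMT ratios do not use it.

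Only precision is at stake. With no test or margin, the ratio and its CI are the whole GMT result on whether MenACYW titers differ when a MenB vaccine is co-administered. A narrower interval at no sampling cost would be welcome.

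**Working it through.** **The plan's own figure.** The plan states no precision or power for these ratios. Its only power figure is 96% for the primary objectives with 89 evaluable per group (SAP 5.5). It reproduces: at least 75 of 89 responders are needed (exact one-sided alpha 0.0248). Power is 99.64% in Group 1 and 95.90% in Group 2, and the product is 95.55%. Adjustment does not touch it.

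**Inputs.**

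- Planned sizes are 200, 100 and 100 (SAP 3.1), with 15% loss (SAP 5.5). If the loss is even, that gives 200 × 0.85 = 170 and 100 × 0.85 = 85. The contrasts are 170 v 85 (Group 1 v 3, Group 1 v 4) and 170 v 170 (Group 1 v pooled 3 and 4).
- Not in the documents, so assumed: the D0-D30 correlation r of log10 titers (0 to 0.5), the SD of log10 titer (0.6), and the shares floored and capped.

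**Formulas** (N = n1 + n2).

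- Unadjusted half-width = t(0.975, N-2) × SD × √(1/n1 + 1/n2).
- Adjusted half-width = t(0.975, N-3) × SD × √((1 - r²)(N-3)/(N-4)) × √(1/n1 + 1/n2).

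For 170 v 85, unadjusted: 1.9694 × 0.6 × 0.1328 = 0.1570, and 10^0.1570 = 1.435. At r = 0.3, adjusted: 1.9694 × 0.6 × √(0.91 × 252/251) × 0.1328 = 0.1500, and 10^0.1500 = 1.413.

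| r | Width ratio, 170 v 85 | CI factor (from ×/÷1.435) | Width ratio, 170 v 170 | CI factor (from ×/÷1.343) |
|---|---|---|---|---|
| 0 | 1.0020 | 1.436 | 1.0015 | 1.343 |
| 0.2 | 0.9818 | 1.426 | 0.9813 | 1.335 |
| 0.3 | 0.9559 | 1.413 | 0.9554 | 1.325 |
| 0.4 | 0.9184 | 1.394 | 0.9179 | 1.311 |
| 0.5 | 0.8678 | 1.368 | 0.8673 | 1.291 |

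The width ratios do not depend on the SD; the CI factors do.

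**Flooring and capping.** Both reduce the usable correlation. In simulated bivariate normal log10 titers with an assumed 50% of D0 values floored and 20% or 40% of D30 values capped:

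- latent r = 0.5 falls to 0.41 or 0.37 (width -9% or -7%);
- latent r = 0.3 falls to 0.25 or 0.23 (width -3% or -2.5%);
- latent r = 0.2 falls to 0.17 or 0.16 (width about -1%).

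With 70% floored and 40% capped, the reduction is 1.7% at latent r = 0.3 and 0.7% at 0.2.

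**Coverage.** With no group difference and 50% floored, equal-variance ANCOVA covered 94.7% to 95.3% in simulation, so the spike at LLOQ/2 does no harm in that case. With a real difference it is less comfortable. If co-administration lowers titers, fewer values in Group 3 or 4 are capped. The smaller group then has the larger variance, and a pooled variance is too small for the contrast. At 170 v 85, 50% floored, simulated coverage of equal-variance ANCOVA was:

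- two-fold drop, 20% capped, r = 0.3: 94.4%;
- two-fold drop, 40% capped, r = 0.5: 93.3%;
- four-fold drop, 40% capped: 92.6% to 92.7%.

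The unadjusted pooled-variance interval did about the same (91.7% to 94.3%), so adjustment is not the cause. HC3 standard errors restored coverage to about 95%.

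**Missing D0 results.** Adjustment loses its advantage once the share without a valid D0 result exceeds 1 - (width ratio)². For 170 v 85 this is 3.6%, 8.6%, 15.7% and 24.7% at r = 0.2, 0.3, 0.4 and 0.5.

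**The case against.** The case for leaving the plan alone is reasonable. The objective is descriptive and no conclusion turns on the CI width. Every size above rests on a correlation, SD and capping rate that the documents do not give. At the lower correlations the gain is trivial: a 2.5% to 3% reduction takes ×/÷1.435 to about 1.42, in an assay read in two-fold dilutions. Baseline already enters through seroresponse and 4-fold rise for the same groups. Objective 5 would also become the only GMT ratio section using ANCOVA, and separate two-group models give Group 1 a different slope in each contrast.

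All of this stands, and it sets the priority low. It does not remove the gain, because the loss if r is 0 is about 0.2% in width.

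A reader might infer more than the documents support:

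- *That the planned ratios are wrong or biased by omitting D0.* They are not. Randomisation makes the unadjusted contrast sound in principle. The reservations are that PPAS2 excludes subjects for deviations that can follow randomisation (SAP 5.2.2), and the coverage issue under capping. Both apply with or without adjustment.
- *That ANCOVA removes chance D0 imbalance.* It reduces it. A covariate floored at LLOQ/2 carries no information on differences below the LLOQ.
- *That the same model should be used for Group 1 v Group 2.* That comparison is not randomised, and the D0 titer there is partly a consequence of the priming vaccine.

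**Conclusion.** This is a cheap, optional improvement in precision. For r between 0.2 and 0.5 the CIs would be about 2% to 13% narrower on the log scale before flooring and capping, and less after. If r is small or capping is heavy, the gain may be near zero. These figures assume 15% loss spread evenly and compare equal-variance intervals with each other. Where HC3 errors widen the interval because variances differ, that widening corrects under-coverage, and the gain should be judged against an unadjusted interval with the same treatment of variance. No test, margin, power or sample size is affected.

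**What to change.** Before database lock, either record that unadjusted ratios were chosen deliberately, or add to SAP 5.1.2.2.5:

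> For each serogroup, the D30 GMTRs and 95% CIs (Group 1 v 3, 1 v 4, 1 v pooled 3 and 4) will be estimated by ANCOVA on log10 D30 titer with group and log10 D0 titer of the same serogroup (computed values), in PPAS2 subjects with a valid D0 titer, using a separate two-group model for each contrast and heteroscedasticity-robust (HC3) standard errors, and back-transformed. Unadjusted GMTs and GMTRs will be shown alongside and labelled.

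For the pooled contrast, Groups 3 and 4 are merged into one group. Do not apply the model to Group 1 v Group 2.

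The cost is one paragraph and a standard model, with no new data. There are three downsides.

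- Subjects without a valid D0 result for a serogroup drop out of that model. The FAS asks only for a post-vaccination result (SAP 5.2.1.1) and missing data are not imputed (SAP 5.3.2). Protocol 5.1.4 makes a missing sample unlikely, but an invalid assay result remains possible.
- Adjusted ratios will not equal the ratios of the tabulated GMTs.
- Three contrasts by four serogroups give 12 ratios; showing both versions gives 24.
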